Overall Study Protocol: 150 systolic HF patients will each undergo an initial clinical and mechanism-oriented assessment battery (involving 2-3 visits, depending on the site where they are enrolled) before and after being enrolled into one of 3 exercise training arms. The pre-/post- evaluations will include 1. a battery of physical function (aerobic and strength) evaluations, 2. serology, 3. muscle biopsy, and 4. DXA scan. The study population will be randomized into one of three 12-week exercise training arms (aerobic, combined aerobic-strength, and inspiratory muscle training [IMT]).

A SAS program will be written to randomly allocate patients to the exercise training arms (see statistics below), also balancing gender and statin-use (90) among these 3 exercise training groups. Enrollment into the exercise training groups will be on a rolling admission.

Notably, we used a 2-3 visit comprehensive assessment protocol as part of our pilot study. It was well tolerated by subjects with no complaints of excessive fatigue or inconvenience. We provided a gap of at least 15 minutes between each of the subparts, with leeway to allow extra time if that is requested by the subject or if it seemed indicated to the study staff. Furthermore, visits were arranged such that assessments requiring physical exertion were alternated with those which are physically non-taxing (e.g., questionnaires done at rest) to help

ensure that the overall protocol was well-tolerated. Heart rate and relative perceived exertion were also checked prior to each subpart of the assessment to confirm that the subject's baseline parameters had been restored before testing proceeded.

Exercise training will be 3X/week, for 60 minutes, over 12 weeks for each of the 3 exercise regimens through a combination of on-site and home-based exercise sessions. Phone calls will be completed weekly by trained exercise based research staff to check in with study patients, work to overcome barriers and modify exercise regimens. Each participant will exercise for a maximum of 12 weeks. If subjects miss training sessions due to intercurrent illness, travel or other reasons, the duration will not be extended as the proposed trial is based on an 'intention to treat' model.

The comprehensive 2-3-visit evaluation (including physical function plus muscle biopsy, and DXA) will be repeated at the end of the exercise training period.

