Expansion into a multi-site protocol: In its first year, the study experienced initial delays as the software necessary for IMT was upgraded to be compatible with newer versions of Windows as well as the VA system. Moreover, even after enrollment began, recruitment of systolic HF patients was more difficult than projected. In response to this challenge, the study will be expanded to multiple sites as well as home based exercise session, each with enhanced recruitment and adherence strategies. This change in study design coincides with [name] plans to transition to the VA Pittsburgh Healthcare System (VAPHS) which will be used to the advantage of the protocol design.

1. [name] will continue as PI of the overall trial as well as site PI at the (VAPHS). Four training arms (Aerobic vs. Strength vs. Combined aerobic-strength, vs. IMT) will be completed at VAPHS, along with pre- and post- skeletal muscle biopsies, bloodwork, DXA and functional assessments. 100 HF patients will be enrolled at that campus, drawing from its robust HF program as well as its extensive HF telehealth database (see recruitment strategies below).
2. The study will also continue at the VABHS where enrollment goals will be 50 HF patients. [name] will assume responsibility as the Boston site PI. Exercise randomization at the VABHS will be limited to aerobic vs. IMT, both to increase efficiencies for the reduced staffing available once [name] and members of his staff have departed for Pittsburgh, and also to ensure adequate enrollment to a RR&D SPIRE-funded 1 I21 RX001423-01A1 substudy (Exercise Training in HF: Structural and Functional Cardiac Remodeling [PI-[name]]) which will explore correlative effects of IMT vs. aerobic training on cardiac remodeling. Also, given [name] role as principal investigator in the ancillary SPIRE study of exercise effects on cardiac remodeling as well as the distinctive skillset required for the echo-based analysis of skeletal muscle perfusion (that is part of the original protocol), both the perfusion and remodeling ultrasound assessments will be studied exclusively at the VABHS. This too is a decision to help maximize local enthusiasm for the protocol, as it becomes a distinctive VABHS goal and responsibility.

Table 4: Outline of protocol (by visit)

Initial Assessment	Visit 1	Informed consent and physical exam, physical functional assessment battery (aerobic, strength, 6MWT, Hand Grip, gait speed, Sit to Stand, and questionnaires)

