	Visit 2 (within one week of visit 1)	Skeletal muscle biopsy; Serology and DXA scan Randomization
	Visit 3 (2-3 days after visit 2) (VABHS only)	Reassessment of biopsy site
Exercise Training	Visits 3/4-38/39	Exercise training sessions (3X/weekly; 60 minutes; 12 weeks)
Post assessment	Visit 39/40-41/43	Post-exercise assessment battery and additional group of assessments completed at visits 1 to 2/3

Table 5: Expansion to a Multi-Site Trial

	Recruitment goals	Exercise arms
VAMC Pittsburgh	100	Aerobic (35), Combined aerobic-strength (30 enrollees), IMT (35 enrollees)
VAMC Boston	50	Aerobic (25 enrollees); IMT (25 enrollees)

Total: 150 HF patients: Aerobic—60; IMT—60; Combined—30;

Study Population

• ***Study Population:*** 150 male and female systolic HF patients with mild-moderate symptoms while on optimal medical therapy will be enrolled. This target will allow for adequate power to address the study objectives even after accounting for a 20% drop-out rate due to attrition and/or suboptimal tissue samples for genetic analysis. Given the expansion to two campuses, and the variation in randomization at each site, the overall proportions of patients enrolled will vary from the original study design but still provide a sound statistical foundation for the anticipated analyses (see statistics section below).

• HF diagnosis will be contingent on a previous hospitalization for HF or physician assessment of HF associated. Each candidate will be examined at the time of enrollment by a cardiologist to ensure that he/she is clinically stable.

• ***Inclusion Criteria:***

- NYHA class II or III for the previous three months despite a minimum of 6 weeks of optimal treatment

- Age \geq 50 years

- Left ventricular EF (LVEF) (by echocardiogram or radionucleotide imaging study within 12 months of enrollment).

- Optimal therapy according to AHA/ACC and HFSA HF guidelines, including treatment with ACEI and beta-blocker therapy (for at least 6 weeks), or have documented reason for variation, including medication intolerance, contraindication, patient preference, or personal physician's judgment.

✓ Patients using aspirin (ASA) will be eligible, but asked to hold the medication for 48 hours prior to biopsy. This technique has previously been used with consistent safety. Patients will also be asked to avoid non-steroidal anti-inflammatory medications (NSAIDs) for 48 hours prior to the biopsy.

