a) *Aerobic vs. Strength vs. Aerobic-Strength regimens will be compared to one another b) Inspiratory Training will be compared to Aerobic-Strength:* In this aim, we compare the combined aerobic-strength training regimen to the single-therapy regimens of aerobic training and strength training, as well as the inspiratory training regimen. These comparisons will be made with changes in the functional outcomes (peak VO₂, 1RM) from baseline as the continuous outcome measures in separate models and training regimen as the categorical predictor in a general linear model, with the following factors considered as potential confounder variables: age, sex, and comorbidities. To limit the type I error rate, only the pre-planned comparisons of the combined aerobic-strength training to the other regimens will be considered. In addition, secondary analyses will consider the following aerobic, strength and inspiratory variables as outcome variables in similar analyses to those outlined above: 6MWT, sit-to-stand, and hand grip strength.

- **Aim 2. To assess gene expression and skeletal muscle perfusion in relation to the different training regimens:** In this aim, we examine the change from baseline to post-exercise regimen in the expression of proteolytic (FoxO and Ubiquitin) and anti-proteolysis (IGF-1 and PGC-1 α) genes as predictors of the change in functional outcomes (peak VO₂, 1RM) over the same period. Separate general linear models for each functional outcome will be performed with gene expression changes as the primary predictor and the following variables considered as potential confounders: age, sex, and comorbidities. As above, a 10% rule for introducing confounding variables and the transformation of outcome variables to deal with regression assumption violations will be considered.

Treatment regimens will also be categorized as those with and without direct skeletal muscle stimulation and this categorical variable will be considered as a predictor of a change in the expression of proteolytic and anti-proteolysis genes in general linear models in a similar fashion to that described above. In addition, similar general linear models will be used with changes in skeletal muscle perfusion as a continuous outcome and aerobic and inspiratory training vs. strength-only training as a categorical predictor with similar potential confounders as noted above.

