Secondary analyses will include assessment of the relative impact of changes in skeletal gene expression vs. changes in perfusion dynamics as predictors of changes in function and quality of life as outcomes. Measures of changes from baseline in serum inflammation, cytokines, and adipokines, and effects of muscle histology will be included as covariates in these analyses. General linear models will be used (outlined above).

Sample size/Power: In this study, we plan to recruit 210 individuals and assign them to one of 4 treatment arms, i.e., randomized between aerobic, aerobic strength, and IMT in VAPHS and between aerobic and inspiratory muscle training in Boston. Sample size calculations are based on 20% attrition over the course of the study. In general, a sample size of 40 per group, using a t-test of independent samples as a simplified model, results in an effect size of 0.64 SD units for 80% power, using a two-sided alpha of 5%.

- **Aim 1:** For this aim, we present calculations for detecting differences in peak VO₂. Previous work by Becker (108) shows a $2.1 \text{ mL O}_2 \cdot \text{kg}^{-1} \cdot \text{min}^{-1}$ change in peak VO₂ in a 6 month aerobic-strength training regimen. Similarly, Tyne-Lenne, et al. shows a $1.1 \text{ mL O}_2 \cdot \text{kg}^{-1} \cdot \text{min}^{-1}$ change in a strength-only regimen (109), HF-ACTION (85) shows a $0.6 \text{ mL O}_2 \cdot \text{kg}^{-1} \cdot \text{min}^{-1}$ change in an aerobic regimen and the IMT trial by Dall'Ago et al. (12) shows a $4 \text{ mL O}_2 \cdot \text{kg}^{-1} \cdot \text{min}^{-1}$ change with inspiratory training. Standard deviations [SD] of the change in peak VO₂ over an exercise regimen are not directly available but using interquartile range values from the largest study [HF-ACTION, n=1442], we obtain a SD value of 2.2 for a 3-month intervention. This would correspond to detecting a difference of $1.26 \text{ mL O}_2 \cdot \text{kg}^{-1} \cdot \text{min}^{-1}$ in any comparison with 80% power, assuming a SD=2.2.

- **Aim 2:** In a similar fashion, a simplified comparison of those with gene expression below the median vs. those above the median would be able to detect a difference of $1.26 \text{ mL O}_2 \cdot \text{kg}^{-1} \cdot \text{min}^{-1}$ in peak VO₂ with 80% power. Analyses of combined training groups facilitates capacity to detect smaller differences between groups.

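### The stated 80% power to detect 1.26 mL/kg/min does not hold for either pre-planned Aim 1 comparison: it is 62% after the plan's 20% attrition and 72% with none

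*Combined protocol and SAP*

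**What the plan says.** **Sample size/Power.** The section says "we plan to recruit 210 individuals and assign them to one of 4 treatment arms", although the randomisation it then describes names only three regimens. It assumes 20% attrition and a two-sided 5% test. It uses an independent-samples t-test as a simplification and says that 40 per group "results in an effect size of 0.64 SD units for 80% power". For Aim 1 it takes an SD of 2.2 for change in peak VO2 and says 1.26 mL/kg/min can be detected "in any comparison with 80% power, assuming a SD=2.2".

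**Design sections.** Overall Study Protocol plans 150 patients: "The study population will be randomized into one of three 12-week exercise training arms". The total under Table 5 reads "Total: 150 HF patients: Aerobic—60; IMT—60; Combined—30". Combined training is offered only in Pittsburgh, and no strength-only arm is allotted. The section on expansion to several sites nevertheless says "Four training arms (Aerobic vs. Strength vs. Combined aerobic-strength, vs. IMT) will be completed at VAPHS". Study Population says the target of 150 is adequate "even after accounting for a 20% drop-out rate due to attrition and/or suboptimal tissue samples for genetic analysis". Limitations again gives 210.

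**Aim 1 analysis.** To limit type I error, "only the pre-planned comparisons of the combined aerobic-strength training to the other regimens will be considered".

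**The concern.** Three parts of the plan do not fit together: the inputs to the power calculation, the arm sizes, and the comparisons that will be tested. The 1.26 figure does not follow from 40 per group. Where it does fit the allocation, it describes a contrast that Aim 1 leaves out.

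This is the only power statement for Aim 1. If the true combined-versus-aerobic difference were 1.26, a reader would expect the trial to miss it 20% of the time. On the stated allocation it would miss it 28% to 38% of the time, so a null result could be read as stronger evidence of no difference than it is.

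**Working it through.** **Inputs.** SD 2.2, two-sided alpha 5%, power 80%, attrition 20% and the t-test model come from Sample size/Power. Arm sizes come from Table 5. The planned comparisons come from the Aim 1 analysis text. Sites are pooled, as that text is written.

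**Formulas.** Standard error of a difference: SE = 2.2 × √(1/n1 + 1/n2). Normal-approximation detectable difference: (1.960 + 0.842) × SE. Unless marked as normal approximation, results below use the noncentral t distribution with n1 + n2 − 2 degrees of freedom.

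**Step 1: the plan's own figures.**
- 40 per group gives 0.634 SD, so the stated 0.64 SD is reproduced.
- In peak VO2 units, 0.64 × 2.2 = 1.41 (exact 1.40), not 1.26. Power at 1.26 with 40 v 40 is 71.6%.
- 210 in 4 equal arms is 52.5 each, or 42 after 20% attrition. That detects 1.36; power at 1.26 is 73.7%.
- 1.26 is reproduced with 48 per group: 2.802 × √(2/48) × 2.2 = 1.258 by normal approximation (1.27 and 79.3% power by t-test).

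**Step 2: which comparison has 48 per group.** 60 × 0.8 = 48, so it is aerobic against IMT under Table 5. Aim 1 is restricted to combined against each other regimen. With no strength-only arm allotted, that leaves combined against aerobic and combined against IMT, each 30 v 60 enrolled.

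**Step 3: power of those two comparisons.** After 20% attrition, SE = 2.2 × √(1/24 + 1/48) = 2.2 × 0.25 = 0.55, and 1.26/0.55 = 2.29. With no attrition, 1/30 + 1/60 = 1/20 = 2/40, so 30 v 60 has the same standard error as 40 v 40.

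| Attrition | Combined v other | Power at 1.26 | Detectable at 80% |
|---|---|---|---|
| 20% | 24 v 48 | 61.8% | 1.56 |
| 10% | 27 v 54 | 67.0% | 1.47 |
| 5% (rate cited for HF-ACTION) | 28.5 v 57 | 69.4% | 1.43 |
| None | 30 v 60 | 71.7% | 1.39 |

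Using the residual degrees of freedom of the three-arm model (117) at 24 v 48 gives 62.3%.

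**Step 4: power at the differences the plan implies.** The cited changes are 2.1 (combined), 0.6 (aerobic) and 4 (IMT).
- Combined v aerobic, 2.1 − 0.6 = 1.5: 76.7% after 20% attrition, 81.5% at 10%, 83.6% at 5%, 85.5% with none.
- IMT v combined, 4 − 2.1 = 1.9: 92.6% after 20% attrition, 96.9% with none.

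**Step 5: Aim 2.** The median split uses all analysed patients: 150 × 0.8 = 120, or 60 v 60. That detects about 1.13, with 87.5% power at 1.26. The stated 1.26 is out of date there, but conservative.

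**Sensitivity only** (analyses the plan does not specify, 20% attrition): adding a site term gives 57.5% power at 1.26 and a detectable difference of 1.64; using Pittsburgh patients only (24 v 28) gives 52.4% and 1.75.

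**The case against.** **The total may be 210.** The power statement sits under 210 patients, and 62% and 72% assume 150. If 210 were split in Table 5's proportions (42 combined, 84 in each other arm), power at 1.26 would be 77% after 20% attrition, 81% at 10%, 83% at 5% and 85% with none. Three equal arms of 70 (56 after attrition) would give 85% and detect 1.18. These figures are correct, but the document states neither split. Under Table 5's proportions the plan's own 20% attrition still leaves power below 80%. The conflict between totals is part of what needs correcting.

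**The 20% overstates the loss for peak VO2.** Study Population counts unusable tissue within the 20%, and peak VO2 needs no tissue. This stands: 62% is the low end. With 150 patients, zero attrition still gives only 72%.

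**1.26 is a detectable difference, not a hypothesised effect.** This stands too, and it limits the consequence. At the implied differences, IMT against combined is well powered, and combined against aerobic falls short of 80% at 20% attrition but not at 10% or less. The plan also says it will weigh results as a whole, but it says so about type I error, which does not guard against over-reading a null.

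**The t-test is a simplification.** Covariate adjustment could reduce the residual SD. The document gives no adjusted value, and 80% power at 24 v 48 would need an SD of about 1.77.

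**Conclusion.** The concern holds. On the only stated allocation, with SD 2.2, a two-sided 5% test and sites pooled, both runnable pre-planned Aim 1 comparisons have 62% power at 1.26 after 20% attrition and 72% with none, against the stated 80%. The corresponding detectable differences are 1.56 and 1.39. The mismatch between 1.26 and the section's own 40 per group needs no choice between 150 and 210 patients.

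The practical shortfall concerns the 1.26 target and combined against aerobic. IMT against combined has more than 90% power at the plan's implied difference of 1.9. This must be fixed, because the plan states a power that its planned comparisons lack.

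**What to change.** 1. Reconcile the two designs: 210 patients or 4 arms (Expansion into a multi-site protocol, Sample size/Power, Limitations) against 150 patients and 3 arms (Overall Study Protocol, Table 5, Study Population). State one total and one split by arm.
2. Remove the claim that the Aim 1 figure applies to every comparison.
3. Replace 40 per group and 1.26 with the detectable difference for each pre-planned comparison at the actual arm sizes, naming the attrition assumed for peak VO2. Under Table 5 this is about 1.56 for combined against aerobic or IMT after 20% attrition, and 1.39 with none. If a different total or split is adopted, recompute.
4. Update the Aim 2 median-split figure to about 1.13 (60 v 60).

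The cost is protocol and SAP wording, and a less favourable power statement for Aim 1. The set of comparisons and the tests stay as planned, and no extra patients are needed to make the correction.

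### The plan's general assurance of adequate power does not hold for skeletal muscle perfusion, which is measured only in Boston (25 aerobic, 25 IMT), where the named contrast has no comparator and the only available one has about 50 to 60% power at 0.64 SD

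*Combined protocol and SAP*

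**What the plan says.** On adequacy, the Study Population section states: "This target will allow for adequate power to address the study objectives even after accounting for a 20% drop-out rate". It adds that, with two campuses and different randomization at each, the proportions enrolled "will vary from the original study design but still provide a sound statistical foundation for the anticipated analyses". Neither sentence excepts any outcome.

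On the basis for power, the Sample size/Power section gives a general case: "a sample size of 40 per group, using a t-test of independent samples as a simplified model", which "results in an effect size of 0.64 SD units for 80% power", at a two-sided 5% level and with 20% attrition. The Aim 2 paragraph gives one figure, for peak VO2 split at the median of gene expression, and then says: "Analyses of combined training groups facilitates capacity to detect smaller differences between groups". No figure is given for perfusion.

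On perfusion itself, Aim 2 of the statistical section names it in its title. It models change in perfusion with a categorical predictor that sets aerobic and inspiratory training against strength-only training. A secondary analysis weighs gene-expression change against perfusion change as predictors of function and quality of life.

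On where it is measured, the section on expansion to multiple sites says that "both the perfusion and remodeling ultrasound assessments will be studied exclusively at the VABHS" (Boston). It sets Boston enrolment at 50 and confines randomization there to aerobic or IMT. Table 5 on the multi-site expansion gives 25 and 25.

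**The concern.** The power basis is 40 patients per group, and the adequacy statement covers all study objectives. Moving perfusion to Boston leaves 50 patients in two arms for that outcome, or 20 per arm after the plan's own 20% loss. That is half the stated basis. Restricting perfusion to Boston was part of the same redesign that the Study Population section describes as statistically sound, yet the power section never mentions it.

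The contrast is a second difficulty. A comparison against strength-only training needs strength-only patients with perfusion data, and Boston randomizes none. The documents disagree on whether Pittsburgh has a strength-only arm (the multi-site text lists one, Table 5 allots none), but perfusion is not measured there in either case. Pooling arms cannot help, because no further arm has perfusion data.

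The trial sets out to sort mechanisms of benefit, and perfusion is one of the two mechanisms it plans to weigh. Readers of the results should know that this one is estimated from a much smaller sample than the general power statement implies.

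**Working it through.** **Inputs.** Two-sided 5% level, 80% power, 40 per group, 0.64 SD and 20% attrition (Sample size/Power); Boston 25 aerobic and 25 IMT (Table 5); perfusion in Boston only (multi-site section). After 20% loss, 25 × 0.8 = 20 per arm.

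**Method.** Two-sample t-test with n per arm and standardized difference d. The noncentrality is d × √(n/2) on 2n − 2 degrees of freedom. Power is the probability that the noncentral t exceeds the two-sided 5% critical value in absolute size.

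**The plan's own figure first.** With n = 40 and d = 0.64, noncentrality is 0.64 × √20 = 2.86 on 78 df, and power is 80.7%. The difference detectable with 80% power is 0.634 SD. The printed 0.64 SD reproduces.

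**The contrast named for perfusion.** Strength-only patients with perfusion data: 0. The contrast cannot be estimated, so it has no power to compute.

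**The only randomized contrast in Boston, aerobic against IMT.**

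| | 20 per arm (20% loss) | 25 per arm (no loss) |
|---|---|---|
| Noncentrality at 0.64 SD | 0.64 × √10 = 2.02 | 0.64 × √12.5 = 2.26 |
| df; critical t | 38; 2.024 | 48; 2.011 |
| Power at 0.64 SD | 50.5% | 60.2% |
| Power, normal approximation | 52.5% | 61.9% |
| Detectable with 80% power | 0.91 SD | 0.81 SD |
| 95% CI half-width, critical t × √(2/n) | 0.64 SD | 0.57 SD |

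The detectable difference is 0.91/0.64 = 1.4 or 0.81/0.64 = 1.3 times the general figure.

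**Perfusion as a predictor of change in function.** By Fisher's z, the correlation detectable with 80% power is tanh[(1.960 + 0.842)/√(N − 3)].
- N = 40 (50 × 0.8): 2.802/√37 = 0.461, so r = 0.43.
- N = 50 (no loss): 2.802/√47 = 0.409, so r = 0.39.
- For scale, an outcome measured at both sites with N = 120 (150 × 0.8): 2.802/√117 = 0.259, so r = 0.25.

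These are unadjusted correlations. No true correlation is assumed, because the documents supply none.

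**The case against.** The strongest reply is that the plan never claims 80% power for perfusion. That is right. The 80% is attached to the general 40-per-group case, to Aim 1 peak VO2, and to peak VO2 by gene-expression split. A reader might infer that a printed perfusion figure is wrong; no such figure exists, and the general figure is arithmetically correct. What remains is that an unqualified adequacy statement covers a named Aim 2 outcome to which its stated basis does not apply.

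A reader might also take the combined-groups sentence as a claim about perfusion. It directly follows the gene-expression statement and does not name perfusion. For gene expression it is plausible. If aerobic and combined training are set against IMT (an assumption about the grouping), (60 + 30) × 0.8 = 72 against 60 × 0.8 = 48 detects about 0.53 SD, below 0.64 and below 1.26/2.2 = 0.57. The sentence needs a limit, not withdrawal.

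The 50% figure needs the whole 20% loss. The Study Population section counts unusable tissue samples for genetic analysis within that 20%, and these would not remove ultrasound data. The fair range is therefore 50 to 60%. That still falls well short of 80%.

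Finally, a reader might infer that a null perfusion result would be taken as evidence against perfusion, or that a p-value from about 120 patients would be set against one from about 40. The documents plan neither. The general considerations put weight on overall results rather than single tests, the gene-against-perfusion analysis is secondary, and one model holding both predictors would, on complete cases, use only Boston patients. The plan does not say which patients that analysis uses, so a clarification is justified, but no misuse should be alleged.

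**Conclusion.** The point stands in a limited form. For perfusion, the general adequacy statement and the 40-per-group basis do not hold. The contrast specified in Aim 2 cannot be estimated from the Boston sample. The only randomized alternative, aerobic against IMT, has about 50% power at 0.64 SD after 20% loss and 60% with none, and 80% power only for 0.91 or 0.81 SD.

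This rests on Boston enrolling 25 per arm as in Table 5, on a simple t-test as in the plan's own model, and on 0.64 SD as the plan's general benchmark; the documents state no expected perfusion effect. The conflict between a total of 150 (Study Population, Table 5) and 210 (Sample size/Power) does not change the Boston figures, because the only site target given for Boston is 50. It would change the 120 used above for scale.

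**What to change.** 1. In Study Population, limit the adequate-power statement to outcomes measured at both sites.
2. In Sample size/Power, Aim 2, state that the combined-groups sentence does not apply to perfusion.
3. In Aim 2 of the statistical section, replace the perfusion contrast with aerobic against IMT in Boston. State what it delivers: about 20 to 25 evaluable per arm, with 80% power for 0.91 to 0.81 SD; and, as a predictor of change in function, 80% power for a correlation of about 0.43 to 0.39 with 40 to 50 patients.
4. Report perfusion results as estimates with 95% confidence intervals.
5. Specify that the gene-expression against perfusion comparison is fitted in the same Boston patients, so that both predictors rest on one sample.

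This costs wording only, with no added patients, visits or procedures. The downside is a less favourable stated figure for perfusion. The strength-only perfusion comparison is given up, but the present design cannot supply it.
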